## **7.4 Implementation of Procedures**

### **7.4.1 Implementation of pre-survey activities**

#### **7.4.1.1 Engage and mobilize stakeholders**

At the beginning of the study, we will systematically identify and engage stakeholders (Provincial and District Health Offices (PHO/DHOs) and other implementing partners) to help build involvement and allow them to participate in the planning of activities for implementation and ensure that their expectations are met.

#### **7.4.1.2 Community engagement and sensitization**

Information about the study will be cascaded to various levels of the community through sensitizations meetings with community leaders such as headmen, teachers and political leaders. Health care providers at all the sentinel sites will be part of the sensitization meetings with the community. Additionally, information about the study will be incorporated in routine health talks which are given to pregnant women as they come to register for ANC.

#### **7.4.1.3 Train DHO staff from sentinel sites**

Health facility in-charges and healthcare workers from the MNCH departments and laboratory hubs will be oriented in the approved study protocol by MOH/CIDRZ research teams and supported throughout the study time. They will also be trained in phlebotomy/specimen collection, labeling and storage, biohazard waste disposal, transfer of specimens, and quality assurance and control. Study staff will also be trained in data collection, documentation, storage and safety, reporting and monitoring. All staff participating in implementation of study activities will be required to obtain good clinical practice and human research protection training. Laboratory staff will be reoriented on running of assays to be used in the study. Additionally, on-site orientation will be conducted to enhance hands-on experience of study procedures. Lay healthcare providers and Peer Educators who have been providing support at the study sites will be selected and trained to provide support for study specific tasks such as participant identification and provision of health education. All staff will be provided with SOPs which will provide them step-by-step instructions on how to perform study procedures.

#### **7.4.1.4 Develop data collection and management tools**

The following standard operating procedures will be developed to provide written step-by-step instructions to help study staff to perform routine tasks at the study sites: screening and eligibility, informed consent, study enrolment, sample collection, handling and testing, data collection and management (questionnaire completion, data entry, security, QA/QC), roles and responsibilities SOP, etc).

In addition, a basic questionnaire will be used to collect information from consented ANC attendees. This questionnaire contains information about symptoms of COVID-19, possible exposures to SARS-CoV-2, and risk mitigation behaviors. Additionally, the questionnaire will collect information on sociodemographic characteristics and routine ANC lab results (HIV, syphilis, Hepatitis B, and malaria).

#### **7.4.1.5 Procure study supplies**

Study sites will be supplied with all required commodities (i.e., assays, lancets, handwarmers, microtainers, dry blood spot (DBS) cards, protective clothing, polyester fiber-tipped applicator, paper towel, waste segregation polythene bag, depressors, cool box, ice packs, bleach, hand sanitizer, scissors, cryovial with virus transport media (VTM), a fine tipped permanent marker, barcodes, bar code scanner, specimen collection and transportation log forms, etc.) to enable them to collect DBS samples for the SARS-CoV-2 serologic tests. The study will outsource tablets for data entry purposes. Laboratories will be equipped with all necessary materials to process and run DBS samples.

### **7.4.2 Implementation of survey activities**

#### **7.4.2.1 Recruitment of study participants**

All study processes will be undertaken as part of routine ANC so as not to disrupt patient flow. Women will be informed of this activity during group health education at the beginning of the first ANC visit. Health education on SARS-CoV-2 will cover symptoms of active infection, testing, and prevention methods, but will emphasize that this study looks for antibodies to SARS-CoV-2 in the blood which are NOT an indicator of current infection.

Women experiencing symptoms of COVID-19 will be managed according to national guidelines (such women will not be recruited in the study because they will not proceed with routine ANC given their acute complaints). Women will be informed that the quality of their antenatal care will not be impacted by their decision whether or not to participate in the study. If they do participate, they will not receive their test results as this study aims to measure population level seroprevalence and does not impact individual clinical care. Women will be approached for consent during individual counseling and testing sessions and blood will be collected on filter paper for a SARS-CoV-2 serologic test using blood from the same finger prick as that for HIV and syphilis testing. While waiting for HIV test results, consenting women will be asked to respond to a short questionnaire. Study participants will then continue with the remainder of the ANC visit as usual.

Sites should have regular access to serological and other routine tests required for care of pregnant women. As a test of past infection, serology results will not be communicated to the facility or participants because they do not affect clinical care (i.e. vaccine eligibility). Any woman that has symptoms of COVID-19 will be referred to relevant testing facility and will follow the national SARS-CoV-2 testing and treatment guidelines. Because they will receive evaluation for their acute complaints per national guidelines, they will not undergo routine ANC services, and, thus, will not be eligible for participation in this study.

#### **7.4.2.2 Sample collection, labelling, storage and courier**

All staff (i.e., study and health facility staff) involved in the collection and transportation of specimen will be trained in safe handling practices and spill decontamination procedures. After obtaining consent from the participant and completing the study questionnaire and while maintaining rapport with the participant, the research nurse or phlebotomy staff will collect blood samples onto a dry-blood spot (DBS) card using finger stick procedures by trained staff. DBS samples collected on filter paper using a standard operating procedure will be used for SARS-CoV-2 antibody detection. Specimen and questionnaires will be labeled at time of collection with an identification sticker that has a pre-printed unique study ID and laboratory specimen ID, and current date. A paper log will be completed by study staff that contains the date, study staff ID, study ID, and a lab label to create a paper

trail in case of mislabeling. This paper log will be stored at the health facility and collected by the study team on a monthly basis. DBS cards will be placed in a bag prior to transportation to district hub laboratories for storage and testing using the existing viral load sample courier system supported by PEPFAR.

DBS cards will be tested for anti-SARS-CoV-2 antibodies using a serologic assay. The specific assay has not been determined yet, as potential cross-reactivity is an emerging issue in Africa [30,31]. Ongoing studies at CDC in Atlanta will inform assay selection. Analyses will be done at a hub or central laboratory. Samples will be kept until the study procedures outlined in the protocol are completed or for up to three years, at which time any remaining samples will be destroyed. The samples will not be used for another purpose than what is stated in the protocol.

Sample analysis will be batched as appropriate; total antibodies or IgG antibodies to SARS-CoV-2 will be assessed using laboratory-based serological assays such as enzyme linked immunosorbent assay (ELISA), immunofluorescence (IFA), chemiluminescent assays (CLIA), multiplexed bead-based assays (the specific assay to be utilized in the study in pending guidance from CDC in Atlanta). All testing will be conducted under appropriate and recommended biosafety conditions per CDC guidance.

## **7.5 Quality control and Assurance activities (supervisory, data and logistics monitoring)**

Project supervisors will review the data collection forms and aggregate results on a monthly basis to assess for completeness, accuracy, and consistency. Periodic site visits will be conducted by the research team to assess for adherence to protocol procedures. Deviation from study protocols will be documented in an incident report and reported to the IRB within three working days. Additionally, up to 20% of samples may be run in duplicate at a central laboratory in Lusaka for the purposes of quality assurance.

## **7.6 Study staff roles and responsibilities**

CIDRZ will support the Ministry of Health/Zambia National Public Health Institute to undertake this surveillance by providing technical assistance, training and mentoring of staff based in the health facilities and DHOs, project oversight, and supplies procurement. The project may be supplemented by PEPFAR funded activities as well as with additional technical support from CDC Zambia. The roles and responsibilities of CIDRZ supported are as outlined:

### **7.6.1 Technical Lead**

The technical lead will be responsible for technical oversight throughout the study period. Before implementation, the technical lead will lead protocol development and submission for ethical approval. The technical lead will participate in developing SOPs and training study staff as well as monitoring data reporting and quality control activities. Upon completion of the study, the technical lead will coordinate preparation and dissemination of the final report.

### **7.6.2 Study Coordinator**

The study coordinator will support study implementation by ensuring that all study activities are being implemented as laid out in the approved protocol. He/she will prepare the ethics application and ensure that study staff are working in compliance with, and be responsible for, tracking the project milestones. The study coordinator will manage the study budget, provide support for recruiting and training of staff. Additionally, he/she will be the point of contact between the principal investigator and staff at study sites.

### **7.6.3 Research Nurse**

One research nurse will be employed for each of the study sites. Their role will be to ensure site compliance with the approved protocol by reviewing regulatory requirements. They will be responsible for communicating information about the study to potential participants and ensuring that staff involved with study implementation have the correct credentials and study related training. The research nurse will draw a blood sample onto filter paper via finger prick for SARS CoV-2 antibody testing and will adhere to sample storage and

transportation procedures. They will also ensure that correct source documents are used and that data is accurately captured in the questionnaires. They will act as the point of contact between the study coordinator and site staff.

#### **7.6.4 Community Health Workers**

Community health workers advocate for underserved communities to receive services and will be engaged from the already existing cadres known at the facility to supplement efforts of MOH HCWs and research nurses. For this study, they will conduct health education to pregnant women attending ANC visits. They will also be trained on how to collect information from the ANC attendees and administer the questionnaire.

#### **7.6.5 Data Coordinator**

The data coordinator will provide support for data management. He/she will ensure that ANC COVID folder on the central server is updated routinely and resolve any problems with the database. He will conduct quality improvement activities and liaise with the study coordinator about any identified quality problems with the data.

#### **7.6.6 Program Assistant**

The program assistant will provide administrative support for the study. He/she will submit request for supply purchases, make regular follow ups about delivery timelines and keep stock of supplies. In addition, he/she will submit cash requests for various activities and ensure that receipts are submitted to the Finance office as per stipulated guidelines. The program assistant will identify venues for trainings and communicate with the vendor about scheduled trainings.

### **7.7 Data collection and management**

The study questionnaire and database will be designed using Open Data Kit (ODK)—a free, open-source suite of tools that will allow collection of data using android mobile devices without Internet connectivity. CHWs will be trained to administer the electronic questionnaire that will be uploaded onto password protected android devices (see appendix IV) which will be piloted to ensure that data is correctly captured and stored when data

collection begins. Individual respondents will be assigned a unique identifier to assist with data confidentiality. Respondents' names and other personally identifying information will not be recorded in the questionnaire. Data will be uploaded to a server after each day of ANC data collection. Data collection devices (tablets, storage card) will be handled only by facility or study staff and kept in a locked office, in a lockable cabinet. Data will be exported to MS Excel for cleaning once every week. Any missing variables will be communicated to the research nurse for follow up and action with the CHW.

## **7.8 Data analysis**

Data will be analyzed on a monthly basis using a statistical program. Basic descriptive statistics, by district, including prevalence point estimates, confidence intervals, and relative standard errors will be tabulated. Variance and confidence intervals will be adjusted for health facility clustering. Prevalence estimates will be disaggregated by sociodemographic variables, routine ANC lab results, and risk factors.

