## 1.0 Introduction

### 1.1 General information on research topic

The novel coronavirus SARS-CoV-2, the cause of COVID-19, was first detected in Wuhan city, China in December 2019 and the first cases were confirmed in Zambia in March 2020.

Current data suggest that as many as 50% of cases are asymptomatic [1]. Initial surveillance has focused primarily on patients with symptoms or severe disease, and, as such, the full spectrum of the disease, including the extent and fraction of mild or asymptomatic infections that do not require medical attention are not clear. Estimates of the case fatality ratio, and other epidemiological parameters, will likely be lower than current estimates once the full spectrum of disease is able to be included in the denominator. With any novel virus, such as SARS-CoV-2, initial population seroprevalence is assumed to be negligible. Thus, antibody seropositivity in a population can allow inferences to be made about the extent of infection, the cumulative incidence of infection in the population, and trends in infection over time.

This protocol proposes to investigate the extent of SARS-CoV-2 infection, as determined by seropositivity, among pregnant women attending 1st antenatal care (ANC) visits, as a surrogate for the prevalence in the general population. The utility of ANC-based surveillance has been established for malaria [2-5], and there is no evidence to date suggesting that pregnant women are at higher risk of contracting SARS-CoV-2 than non-pregnant adults, suggesting that ANC-based surveillance could provide useful information for monitoring the spread of SARS-CoV-2 over time [6]. This will be a non-randomized assessment of the potential to leverage pregnant women attending 1st ANC as a pragmatic sentinel population to monitor prevalence of SARS-CoV-2 and to detect changes in transmission in selected areas.

As the Zambian Ministry of Health (MOH) continues to focus on controlling and mitigating further spread of the SARS-CoV-2 through active surveillance for case detection, contact tracing, physical distancing and isolation while strengthening case-based management, it is important to build a national SARS-CoV-2 surveillance system that is crucial for containing transmission of the virus and preparing for future waves of the infection.

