## **1.2 Overview of research and research gaps**

This surveillance platform may be able to provide key information on the spread of the SARS-CoV-2 virus through the general population. By using serologic testing to understand trends in the proportion of pregnant women over time who were exposed to SARS-CoV-2, we will be able to understand not only the ultimate proportion of pregnant women who were ever infected, but also be able to track and potentially detect outbreaks (e.g. in areas with increasing positivity rates), unlike data that would be available from a single cross-sectional survey, which could give the overall prevalence at a single point in time. In most places to date, testing has focused on symptomatic people, their contacts or others considered at high risk for infection, but there is limited understanding of the true proportion of asymptomatic cases.

There are gaps in information about the prevalence and clinical characteristics of SARS-CoV-2 in Zambia. We propose to conduct SARS-CoV-2 sentinel surveillance among first-time ANC attendees in selected Maternal, Newborn and Child Health (MNCH) departments in four districts (Lusaka, Chongwe, Chadiza and Chipata) of Lusaka and Eastern provinces to assess SARS-CoV-2 seroprevalence. Pregnant women will serve as a proxy for the healthy adult population of these districts, much as they have in sentinel surveillance for HIV and malaria. Because we will use serologic testing from blood and not nasal swabs, this collection will not substantially alter the risk for either the health worker nor the woman and will not deplete the supplies of SARS-CoV-2 Polymerase chain reaction (PCR) reagents used for diagnosis.

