### 6.2 Primary Objectives

- 6.2.1 To estimate on a monthly basis the seroprevalence of SARS-CoV-2 among pregnant women aged 15-49 years attending their first ANC visit at selected health facilities in Chadiza, Chipata, Chongwe, and Lusaka districts of Eastern and Lusaka Provinces.
- 6.2.2 To monitor trends in SARS-CoV-2 seroprevalence in the selected districts.

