### 7.3.2 Sample Size

All pregnant women who meet the eligibility criteria presenting at the study sites will be approached for participation into the study. Monthly ANC attendance varies by district, as shown in Table 2. Study districts will be expected to recruit 200 pregnant women per month. The estimated seroprevalence is expected to vary by study site, as prevalence has been demonstrated to be different between urban and rural locations in Zambia [7]. A sample size of 200 women per district per month will be sufficient to detect a range of estimated proportions of SARS-CoV-2 seroprevalence (Figure 1). The confidence interval (CI) reflects the bounds of the true seroprevalence of COVID-19 among pregnant women attending ANC (and not the overall pregnant women population or general population). Where prevalence is expected to be low (i.e. rural districts), a sample size of 200 women produces a 95% CI half-width of 2.4% for 3% seroprevalence (lowest estimate). Where prevalence is expected to be higher (i.e. urban districts), a sample size of 200 women produces a 95% CI half-width of 7.0% for 50% seroprevalence. Women will be recruited evenly throughout the month from study sites selected for each district. If the monthly recruitment target is met, study sites will be expected to pause sample collection and reconvene at the start of the next month.

Table 2: Average monthly number of first ANC attendees using PMTCT_STAT denominator	
District	Average monthly ANC attendance
Chadiza	424
Chipata	759
Chongwe	653
Lusaka	6,378

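### Section 7.8 adjusts the monthly district prevalence for facility clustering only, so false positives from an assay left open over cross-reactivity stay in the point estimate

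*Protocol*

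**What the plan says.** The monthly analysis is set out in section 7.8: "Basic descriptive statistics, by district, including prevalence point estimates, confidence intervals, and relative standard errors will be tabulated". The only adjustment stated there is "Variance and confidence intervals will be adjusted for health facility clustering". Nothing is stated that acts on the point estimate.

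The estimate serves primary objective 6.2.1: "To estimate on a monthly basis the seroprevalence of SARS-CoV-2 among pregnant women aged 15-49 years attending their first ANC visit".

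On precision, section 7.3.2 says "a sample size of 200 women produces a 95% CI half-width of 2.4% for 3% seroprevalence (lowest estimate", and gives 7.0% at 50% seroprevalence for the same 200 women.

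On the test, section 7.4.2.2 says "The specific assay has not been determined yet, as potential cross-reactivity is an emerging issue in Africa", and continues: "Ongoing studies at CDC in Atlanta will inform assay selection". No sensitivity or specificity appears anywhere in the protocol. Section 7.5 allows up to 20% of samples to be run in duplicate for quality assurance.

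**The concern.** The protocol names a threat to specificity and then states an estimator that passes it through unchanged. A cross-reacting sample is counted as positive although it holds no SARS-CoV-2 antibody, so the error affects seroprevalence itself, which is what objective 6.2.1 asks for.

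None of the measures described removes this:

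- The clustering adjustment widens the interval but leaves it centred on the same value.
- Assay selection may reduce the error but does not guarantee that it is zero.
- Duplicate runs measure repeatability. A sample that cross-reacts repeatably is positive both times.

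At stake is the level reported for low-prevalence districts, which section 7.3.2 expects to be the rural ones. There, a small false-positive rate acts on nearly all the women tested, and true positives are few.

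**Working it through.** **Inputs.** From section 7.3.2: n = 200 per district-month, true prevalence p = 3% and 50%, quoted half-widths 2.4 and 7.0 points. Sensitivity (Se) and specificity (Sp) are not in the protocol, so all values below are assumptions.

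**Step 1. Reproduce the quoted half-widths**, using 1.96 × √(p(1−p)/200):

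- p = 3%: 1.96 × √(0.03 × 0.97/200) = 2.36 points (quoted 2.4).
- p = 50%: 1.96 × √(0.5 × 0.5/200) = 6.93 points (quoted 7.0).

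These are plain binomial figures with no test-error term.

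**Step 2. Effect of imperfect specificity alone** (Se = 100%), the error that the protocol itself raises. Apparent prevalence = p × Se + (1−p)(1−Sp). For example, at p = 3% and Sp = 98%: 0.03 + 0.97 × 0.02 = 4.94%, of which 0.0194/0.0494 = 39% is false.

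| Assumed Sp | True 3% appears as | Bias, points | False share of positives | True 50% appears as |
|---|---|---|---|---|
| 99% | 3.97% | +0.97 | 24% | 50.5% |
| 98% | 4.94% | +1.94 | 39% | 51.0% |
| 97% | 5.91% | +2.91 | 49% | 51.5% |

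At 97% the bias exceeds the quoted half-width of 2.4 points. At 99% it is well inside it. At 99.5% (Se 100%) the apparent value is 3.49%. For Sp from 99.5% to 100% and Se from 80% to 100%, the bias at 3% stays within about 0.6 points in either direction.

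**Step 3. If sensitivity is also imperfect**, which the protocol does not raise. Apparent prevalence can be written p × (Se + Sp − 1) + (1 − Sp), so any true change is multiplied by Se + Sp − 1. With Se 80-90% and Sp 97-99%, this factor is 0.77-0.89. A true 10-point change then appears as 7.7-8.9 points, and a true 50% as 40.5-46.5%. With Se = 100% the factor is 0.97-0.99 and the shrinkage is trivial. In either case the direction of a trend survives if test performance is constant.

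**Step 4. Precision after correction.** The Rogan-Gladen estimate is (apparent + Sp − 1)/(Se + Sp − 1), and its half-width is the apparent half-width divided by (Se + Sp − 1) when Se and Sp are taken as known. At a true 3%, n = 200, Se = 100%, before clustering:

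- Sp 99%: 1.96 × √(0.0397 × 0.9603/200) = 2.71; 2.71/0.99 = 2.7 points.
- Sp 97%: 1.96 × √(0.0591 × 0.9409/200) = 3.27; 3.27/0.97 = 3.4 points.

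If Se and Sp are themselves estimated, the interval widens further. With Se 90% and Sp 98%, each from an assumed 200 reference samples, the half-width at 3% is 3.9 points, against 3.3 with both known.

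**Step 5. How often the corrected estimate is zero or truncated to zero.** This happens when the number of positives is at most 200 × (1 − Sp). At a true 3% and Se = 100%, the binomial probability of at most 2 positives (Sp 99%, apparent 3.97%) is 1.3%, and of at most 6 (Sp 97%, apparent 5.91%) is 4.6%. With Se 80-90% the range is 2-9%, and 11-22% if clustering halves the effective sample to 100.

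**The case against.** The strongest reply is that this is a matter for the statistical analysis plan. A correction needs the performance data of a named assay, none is named yet, and section 7.8 is a short outline that never says the estimates will be uncorrected. Much of that stands: a correction may exist in a plan not shown, and nothing in the sampling or collection forecloses one, since it is a transformation of the crude figure. But section 7.8 does address adjustment and names only one kind, while the protocol itself raises cross-reactivity. Stating the rule now, before assay and data are in hand, costs little.

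The second reply is that deferring the assay choice is itself the remedy. It is a real safeguard. If it yields specificity of 99.5% or more, the bias at 3% is small.

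Three stronger readings are tempting and are not supported:

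- **That the half-widths in section 7.3.2 are wrong.** They are correct binomial figures and need only a label. That section also describes the interval as bounding the true seroprevalence among ANC attendees, but the sentence mainly defines the target population and says nothing about test error.
- **That the plan fails to deliver what it promises as "the ultimate proportion of pregnant women who were ever infected".** Those words come from background section 1.2. The research question, aim and primary objectives are framed as seroprevalence, and section 1.1 qualifies its own wording: "investigate the extent of SARS-CoV-2 infection, as determined by seropositivity". A test-performance correction alone would not give the proportion ever infected either, because it does not separate vaccine-induced antibody, although vaccination history is on the questionnaire.
- **That urban estimates are badly biased or their intervals fail.** That needs sensitivity of about 80-90%, which the protocol never suggests. With specificity error alone, the effect at 50% is at most 1.5 points.

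**Conclusion.** The point holds as a cheap improvement. Followed as written, section 7.8 gives a point estimate that includes false positives, and its one stated adjustment cannot remove them. Under assumed specificity of 97-99% with perfect sensitivity, the upward bias is 1.0-2.9 points at a true 3% and 0.5-1.5 points at 50%. With specificity of 99.5% or more, it is at most about 0.6 points at 3%. The size therefore depends wholly on the assay still to be chosen and matters mainly in low-prevalence districts. Attenuation of trends and of high-prevalence estimates is conditional on imperfect sensitivity, which is an added assumption here.

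**What to change.** In section 7.8, state that each district-month prevalence will be reported both crude and adjusted for test performance (Rogan-Gladen truncated to 0-1, or a Bayesian equivalent). The adjustment should use the available sensitivity and specificity data for the chosen assay and carry their uncertainty into the cluster-adjusted interval. In section 7.3.2, add that the quoted half-widths refer to apparent seropositivity with a perfect test. Say also that the adjusted figure is an antibody prevalence and not, by itself, the proportion ever infected.

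The cost is a sentence or two in each section and a standard calculation once the assay is known; no extra samples or visits are needed. The price is wider intervals (about 2.7-3.4 points at 3% in place of 2.4, under the specificity-only assumptions and before clustering) and some low-prevalence estimates truncated to zero. That is why the crude figure should stay alongside. The adjusted figure will be only as good as the assay data behind it.
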